- (2) **Control Conditions Hypothesis:** We hypothesize significant differences in signal intensity across the three different epoch conditions—TM, passive-attending and mental-counting. Specifically, de-excitation will be maximum for TM, then passive-attending, and lastly, mental-counting.

Aim 2: Maximum De-excitation Meditation Substate. We predict that event-related (er-fMRI) and state-related (sr-fMRI) analytic procedures will yield distinct spatial and temporal patterns of BOLD intensity that characterize the maximum de-excitation substate associated with spontaneous breath-quiescent periods (SBQ, breath period > 10 sec). We will test five hypotheses in this experiment.

- (3) **IBH-Blood Gas Hypothesis:** Using event-related-fMRI, we hypothesize moderate changes in blood gas changes will be detected during Intentional Breath-Holding (IBH), and blood gas levels will be significantly correlated with changes in BOLD signal intensity, consistent with published findings.
- (4) **SBQ-Blood Gas Hypothesis:** Using event-related-fMRI, we hypothesize small changes in blood gas changes will be detected during Spontaneous Breath Quiescence (SBQ), and blood gas levels will not be significantly correlated with changes in BOLD signal intensity.
- (5) **SBQ-IBH Hypothesis:** Using event-related-fMRI, we hypothesize that specific spatiotemporal patterns of BOLD signal will be associated with onset of SBQ, and will differ from IBH control periods in terms of reduced BOLD signal of the anterior cingulate cortex and brainstem during SBQ.
- (6) **SBQ-Controls Hypothesis:** Using state-related-fMRI, we hypothesize that BOLD signal intensity patterns during SBQ periods will differ from two control conditions—IBH periods, and eyes-closed periods (as defined in Aim 1, either passive-attending or mental-counting).
- (7) **SBQ-Non-SBQ Hypothesis:** Using state-related-fMRI, we hypothesize that BOLD signal intensity patterns during SBQ periods will differ from the scans during non-SBQ periods during meditation.

B. BACKGROUND AND SIGNIFICANCE

B.1. Need for Basic Neuroscience Research on Mechanisms of CAM Modalities.

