D.6.1.1 IBH-Blood Gas Hypothesis. Using event-related-fMRI, we hypothesize moderate changes in blood gas changes will be detected during Intentional Breath-Holding (IBH), and blood gas levels will be significantly correlated with changes in BOLD signal intensity, consistent with published findings.

D.6.1.2 SBQ-Blood Gas Hypothesis. Using event-related-fMRI, we hypothesize small changes in blood gas changes will be detected during Spontaneous Breath Quiescence (SBQ), and blood gas levels will not be significantly correlated with changes in BOLD signal intensity.

D.6.1.3. SBQ-IBH Hypothesis. Using event-related-fMRI, we hypothesize that specific spatiotemporal patterns of BOLD signal will be associated with onset of Spontaneous Breath Quiescence (SBQ), and will

differ from IBH control periods as marked, in particular, by reduced BOLD signal of the anterior cingulate cortex and brainstem during SBQ.

D.6.1.4. SBQ-Controls Hypothesis. Using state-related-fMRI, we hypothesize that BOLD signal intensity patterns during SBQ periods will differ from two control conditions—IBH periods, and eyes-closed periods (as defined in Aim 1, either passive-attending or mental-counting).

D.6.1.5. SBQ-Non-SBQ Hypothesis: Using state-related-fMRI, we hypothesize that BOLD signal intensity patterns during SBQ periods will differ from the scans during non-SBQ periods during meditation.

D.6.2. Issues.

The second phase of the grant will systematically explore neural patterns underlying the second principal substate during TM practice—periods of SBQ with durations of 10 to 40 sec—signifying the maximum de-excited state of TM practice. A study of breath-quietness raises a number of possible confounds.

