The BOLD signal and physiological measures will be collected during four runs of 12 minutes duration each. Each 12 min run comprises three periods: 5 min uninterrupted meditation, 5 min structured breath-holding, and 2 mins non-task, eyes-closed (EC) control. The meditation period are free running with no interruptions from experimenters. During the meditation period we expect 3-5 SBQ periods. The breath-holding periods are structured by duplicating the previous SBQ pattern by voice command from experimenter, the onset and offset of IBH corresponding to SBQs time frame for each subject. The non-task control period will be determined from the outcome of experiment 1 (Aim 1), and either be passive-attending or mental-counting. The physiological measures will include respiration and transcutaneous CO₂ measurements. Four runs will take 48 minutes, or about 1 hr due to 30 rest periods between conditions. Therefore, each fMRI session will last about 90 minutes per subject.

D.6.4. Event-related fMRI analysis (Hypotheses 1-3).

Er-fMRI methodologies will be used to probe brain mechanisms during the onset of two conditions, during SBQ and IBH periods. The scans will be aligned relative to the onset of either SBQ or IBH during the four runs to permit signal averaging: 4 images before (12 secs) and 4 images after onset (12 secs). A TM meditator, selected in our screening protocol, may exhibit 25-30 spontaneous breath-quiet periods in a 30-min TM session [9, 20-22]. We estimate 12-20 periods will occur in our four meditation periods.

Images from individual runs will first be normalized to correct for the range of intra- and inter-subject signal intensity and temporal drift [171]. Specifically, normalization will involve: (1) scaling of signal intensity to a fixed value of 1000; (2) linear slope removal in a voxel-by-voxel basis; (3) spatial filtering with a one-voxel radius Hanning filter, and; (4) removal of the mean signal intensity on a voxel-by-voxel basis. The normalized fMRI images will then be aligned relative to the onset either SBQ or IBH periods. These images will be averaged within each subject. The mean image for each subject will be transformed into stereotaxic atlas space [208] using the highest point of the mid-sagittal plane and the anterior and posterior commissures. The atlas-transformed matrices will then be averaged across subjects.

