- We expect minor blood gas changes and hence, few significant correlations between CO₂, with BOLD signal during spontaneous breath-quietness.

D.6.4.3. Neuroimages during SBQ and IBH. Er-fMRI will be compared between IBH and SBQ periods, using a repeated measures MANOVA.

- We expect main effects for brain areas. Animal hypercapnia [209] and human breath-holding [157, 203, 210, 211] studies indicate that hypercapnic conditions are associated with global increases in most cortical and subcortical grey matter blood flow. Thus, we expect region-independent, nonspecific activation in all areas during IBH. In contrast, we expect region-dependent, specific activation or deactivation of BOLD signal intensity during SBQ.
- We expect main effects for the repeated measures, indicating significant differences in signal intensity across time.
- We expect no significant interactions.

D.6.5. State-related fMRI analysis (Hypotheses 4-5).

Sr-fMRI methodologies will be used to probe brain mechanisms during SBQ, IBH, and control periods. In the previous three analyses, we identified brain areas that displayed significant time-locked relation to the onset of both IBH and SBQ. A complementary approach to identification of brainstate changes is the use of state-related methodology. This method divides the time-series into condition-specific bins for comparison. Scans collected in Expt. 2 will be categorized into six bins: before and during either IBH, SBQ or equal-length periods during eyes-close (EC) control. Scans assigned to each bin will be compared by multiple linear regression, correcting for differences in blood gas levels across the three conditions.

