D.6.5.1. Sequence of Analysis. First, we will create a dummy time-series of 1, or 2's that correspond to the scans before and during three conditions: IBH, SBQ or EC. The dummy time-series then will be convolved with the hemodynamic response model using the Cohen Model. This will yield the dummy independent variable that will be entered into the multiple linear regression analysis along with O₂ and CO₂ data. The scans for each of the periods will be dependent variables in the analysis. We will examine the resulting statistical parameter maps for clusters of pixels displaying significant fluctuations in signal intensity. The Z-statistic of the activated clusters that meet our criteria (D.2.3.) will be entered as variates in a repeated-measures ANOVA, with brain area as the factor and the period as the repeated measures.

D.6.5.2. Comparison between conditions: SBQ, IBH and EC. Condition differences will be assessed with two-way repeated measures ANOVA with brain areas and condition as factors, and the two periods (before and during the conditions) as the repeated measures. Individual comparison will be conducted if there are significant main effects.

- We expect no main effects for brain areas, indicating highly variable activation across brain areas yielding no consistent relations.
- We expect main effects for condition (SBQ, IBH, EC), indicating different brain mechanisms are active during each condition. For example, during IBH we expect higher levels of task effort and motor system activation, and possibly higher CO₂ levels to yield the predicted main effect.
- We expect main effects for the repeated measure (before and during). The 'before' periods may be somewhat similar, while the 'during' periods may be significantly different.
- We expect significant interactions, indicating differential involvement of some brain areas during the three conditions. For instance, the cerebral cortex may exhibit lower BOLD signal in both 'before' periods. However, the cortex is expected to be activated during IBH, while remaining low or reduced during SBQ.

D.6.6. Outcome. This experiment will help identify:

- (1) Neural mechanisms specific to the generation and maintenance of IBH, and the effects of hypercapnia and loss of mechanical respiratory activity on BOLD signal intensity.
- (2) Neural mechanisms specific to SBQ periods, as compared to a variety of brainstates, including, other meditation periods, IBH, and EC.

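### Hypothesis 6 is about scans during SBQ, but D.6.5.2 draws its condition inference from a main effect that averages 'before' and 'during' scans, so a standing meditation-versus-control difference can pass for an SBQ effect

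*Protocol*

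**What the plan says.** Hypothesis 6 (Protocol section A and D.6.1.4) states: "we hypothesize that BOLD signal intensity patterns during SBQ periods will differ from two control conditions". The two controls are IBH periods and an eyes-closed task carried over from Aim 1.

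D.6.3 takes the three conditions from separate stretches of each run: "Each 12 min run comprises three periods: 5 min uninterrupted meditation, 5 min structured breath-holding", followed by 2 minutes of eyes-closed control. The control task will be passive-attending or mental-counting, depending on Experiment 1.

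D.6.5 forms the bins: "Scans collected in Expt. 2 will be categorized into six bins: before and during either IBH, SBQ or equal-length periods during eyes-close (EC) control". D.6.5.2 then specifies a "two-way repeated measures ANOVA with brain areas and condition as factors, and the two periods (before and during the conditions) as the repeated measures". It gives four expectations: no brain-area effect, a condition effect, a before/during effect, and interactions. The condition effect carries the interpretation: "We expect main effects for condition (SBQ, IBH, EC), indicating different brain mechanisms are active during each condition". The example offered is that "during IBH we expect higher levels of task effort and motor system activation, and possibly higher CO₂ levels to yield the predicted main effect". Individual comparisons are to follow significant main effects; no other trigger is named.

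D.6.5.1 describes the variate differently. A dummy series of 1s and 2s for scans before and during each condition is convolved with the response model and regressed with the O₂ and CO₂ data. The Z-statistics of qualifying clusters then go into the ANOVA.

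**The concern.** The hypothesis is about *during* scans, whereas the condition main effect gives the *before* scans equal weight. Scans before an SBQ lie in the meditation block, scans before a breath-hold in the breath-hold block, and scans before an EC period in the control block. Each *before* bin therefore carries its own block's level into the condition mean.

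Hypothesis 2 already predicts that meditation differs from both candidate control tasks. On the protocol's own theory, then, a significant condition effect is likely even if nothing happens at SBQ. D.6.6 promises neural mechanisms specific to SBQ periods, and a significant result on this term could not be credited to them.

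**Working it through.** The protocol gives no power figure, effect size or variance for this test, so there is no stated figure to reproduce. The check is algebra, followed by an illustration under stated assumptions.

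**Algebra.** For condition c let b be the *before* level, d the *during* level, and Δ = d − b.

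- Condition mean: m = (b + d)/2 = b + Δ/2.
- Condition contrast: m(SBQ) − m(EC) = [b(SBQ) − b(EC)] + ½[Δ(SBQ) − Δ(EC)].

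Three cases, in SD units, with IBH and EC at 0 throughout:

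| Case | SBQ before, during | Pooled contrast | *During* contrast | Change contrast |
|---|---|---|---|---|
| A. Block shift, SBQ inert | −1, −1 | −1 + ½(0) = −1 | −1 | 0 |
| B. SBQ change, equal *before* levels | 0, −1 | 0 + ½(−1) = −0.5 | −1 | −1 |
| C. SBQ change, offsetting *before* level | 0.5, −0.5 | 0.5 + ½(−1) = 0 | −0.5 | −1 |

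The pooled contrast is at its largest where SBQ does nothing and vanishes in a case where SBQ does something.

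**Rejection rates with SBQ inert.** Inputs: n = 10 (D.4.3). Assumed: unit within-subject SD per cell, independent errors, alpha 0.05, and the meditation block shifted equally in both bins.

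| Block shift (SD) | Condition main effect | Both follow-ups on pooled means, gated | Condition × period |
|---|---|---|---|
| 0.5 | about 30% | about 13% | about 5% |
| 0.75 | about 62% | – | about 5% |
| 1.0 | about 86% | about 68% | about 5% |

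A second set of assumptions (six areas averaged, residual SD 1, subject SD 1, subject-by-condition SD 0.5) gives 42% and 96% for the main effect at shifts of 0.5 and 1 SD, again with 5% for condition × period. In the same runs the SBQ-EC contrast on *during* scans rejects 34% and 86%, and the SBQ-EC change contrast 5%.

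**Dilution (case B).** With independent unit errors, the SD of each contrast per subject is:

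- Pooled: √(½ + ½) = 1, so effect/SD = 0.5/1 = 0.50.
- *During* only: √(1 + 1) = 1.41, so 1/1.41 = 0.71.
- Change: √(2 + 2) = 2, so 1/2 = 0.50.

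Pooling therefore loses sensitivity against the *during* contrast. Against the change contrast it loses none in this model, because the signal and the noise both halve. Where subjects also differ in their standing condition levels, that variation cancels from change but not from the pooled mean. Under the second set of assumptions, case B gives 43% power for the main effect, 87% for the *during* contrast and 93% for the SBQ-EC change contrast. In case C the main effect falls to 5%, while the change contrast stays at 92%.

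**The case against.** Four points can be made for the plan.

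*Interactions are already expected.* This is true. D.6.5.2 expects significant interactions, and its cortex example (low in the *before* periods, raised during IBH, low during SBQ) is in effect condition × period. It also expects *before* periods to be somewhat similar and *during* periods to differ. A reader might infer that the plan has no term for an SBQ change; the text does not support that. What stands is that the interaction is described as brain areas differing across conditions, is not tied to Hypothesis 6, and does not open the individual comparisons. The similarity of *before* levels is hoped for, not tested.

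*Hypothesis 6 compares levels.* As worded, it does: "BOLD signal intensity patterns during SBQ periods will differ from two control conditions". A standing difference between SBQ scans and EC scans would satisfy it, and SBQ against the rest of meditation is the separate Hypothesis 7 (D.6.1.5). So the rejection rates above are not false positives for the literal hypothesis, and it would be too strong to say that Aim 2 loses all substate specificity. Even so, the literal hypothesis concerns *during* scans only, and a level difference cannot support an SBQ-specific mechanism.

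*Breath-holding alone could trigger the effect.* A reader might infer from the plan's own IBH example that a change confined to IBH would be reported as an SBQ finding. With only IBH *during* raised by 1.5 to 3 SD, the main effect does reject 61% to over 99%. But requiring both planned follow-ups (SBQ-EC and SBQ-IBH) brings this down to 3–5%, while omnibus condition × period fires as often as the main effect (61–99.6%). The planned comparisons already deal with this case, and it is no part of the point.

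*The variate may already be a change score.* If the Z from the 1/2 dummy codes *during* against *before*, a condition effect on that Z is the change test. But there would then be one Z per condition, and the model could not take "and the two periods (before and during the conditions) as the repeated measures". The two sections cannot both be followed as written.

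The protocol also does not say which means the individual comparisons use. Pooled means are the natural reading of a follow-up to a main effect, but that is an inference.

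**Conclusion.** The point holds in this form. The condition main effect in D.6.5.2 mixes a difference between blocks with half of any difference in change, so it is contaminated and diluted as evidence about SBQ. It is not a pure block comparison, since it does carry part of an SBQ effect.

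Under an assumed unit SD and n = 10, a meditation-block shift of 0.5 to 1 SD with SBQ inert makes the main effect significant about 30% to 86% of the time, and both gated pooled follow-ups about 13% to 68%, against about 5% for condition × period. The shifts and variances are assumptions, and the percentages move with them. The contamination itself follows from the algebra and needs only unequal *before* levels. The power lost for a real SBQ change depends on the variance structure: it is clear against a *during*-only contrast, but against a change contrast it appears only when subjects differ in standing condition levels.

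These figures assume that the variate has separate *before* and *during* values, as D.6.5.2 states. If D.6.5.1 already yields a change score, the fault is the conflict between the two sections.

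**What to change.** In D.6.5.2:

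1. Do not read the condition main effect as evidence about SBQ. Report it as a block-level comparison of meditation, breath-holding and control.
2. Test Hypothesis 6 with two planned within-subject contrasts, SBQ-EC and SBQ-IBH, not gated on the main effect and both required.
3. Compute them on *during* scans for the hypothesis as worded. Compute them on change, such as (SBQ during − before) − (EC during − before), for any claim of a mechanism specific to SBQ. The *during* contrast alone does not support that claim, because it too responds to a standing block difference.
4. Reconcile D.6.5.1 with D.6.5.2. State whether each Z refers to one bin or to *during* against *before*. If the latter, remove period as a repeated measure and name the condition effect on that Z as the change test.

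The cost is wording and a few contrasts on scans already planned. The downside is noise: with independent unit errors, the change contrast has an SD of 2 against 1 for the pooled contrast. Both contrasts must also succeed, so fewer results will be significant.
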